2.2.2 DSMB analyses

The DSMB is responsible for reviewing the data during the study on an independent basis to ensure subject safety at some specific steps. The DSMB will make recommendations concerning the conduct of the study.

Details on DSMB activities are described in the DSMB-Charter and the DSMB-SAP.

3 STUDY OBJECTIVES

The objectives of this study are

- To evaluate the safety and efficacy of Viaskin Milk after 12 months of epicutaneous Immunotherapy (EPIT) treatment, for desensitizing Immunoglobulin E (IgE)-mediated cow's milk-allergic children.
- To assess the long-term safety and efficacy of up to 48 months of treatment with Viaskin Milk.

This document is confidential

Statistical Analysis Plan

- To assess the safety and the therapeutic benefit of the most effective tested dose of Viaskin Milk over 24 months of treatment.

3.1 BRIEF DESCRIPTION

MILES study (V135-201) is a multi-centre, double-blind, placebo-controlled, randomized trial to study the safety and efficacy of Viaskin Milk applied epicutaneously every day to subjects from 2 to 17 years of age with IgE-mediated cow's milk allergy (CMA). Viaskin Milk is a patch containing an extract of cow's milk proteins. The placebo treatment consists of a Viaskin Milk patch containing a similar formulation without cow's milk proteins.

Subjects received blinded treatment for 1 year at one of the 3 doses of Viaskin Milk: 150 μ g, 300 μ g, or 500 μ g, or placebo. After the first year, all subjects received the highest dose of Viaskin Milk 500 μ g, and continued treatment in an open-label manner for up to a maximum of 3 additional years. Following results of the 12-month blinded period, all eligible subjects who wish to continue participation in the study were switched from Viaskin Milk 500 μ g to Viaskin Milk 300 μ g dose for 24 additional months of treatment.

The study is conducted at 17 sites in the United States and Canada, with selected investigators and staff experienced in the diagnosis and management of CMA and anaphylaxis, and who are capable of performing a DBPCFC in children (2 to 11 years old) and adolescents (12 to 17 years old).

Eligible subjects with confirmed IgE-mediated CMA performed a first DBPCFC at screening with escalating doses of cow's milk proteins. Subjects showing a positive DBPCFC at screening, defined as the appearance of objective signs or symptoms to an eliciting dose of cow's milk proteins \leq 300 mg (approximately 9.4 mL of cow's milk) were randomized in the study.

The study was divided into 2 consecutive parts for randomization of the subjects to treatment: Part A and Part B. Part A permitted an evaluation of the safety of 3 escalating doses of Viaskin Milk (150 μ g, 300 μ g, and 500 μ g cow's milk proteins) versus placebo in successive cohorts of subjects prior proceeding to Part B. Part B was designed to evaluate the efficacy and safety of the 3 selected safe doses (as determined from Part A) of Viaskin Milk versus placebo.

The efficacy of Viaskin Milk was assessed based on data pooled from subjects in both Part A and Part B. Details of subject enrolment and the treatments administered for each part of the study are provided in [Section 3.4](#).

Subjects from both Part A and Part B were randomized to receive treatment with Viaskin Milk or placebo for 12 months (randomized double-blind treatment period), after which a second DBPCFC was performed. The primary analysis of this study was conducted after data have been collected up to Month 12 visits including both days of the DBPCFC at Month 12. Consequently, results from the safety and efficacy data collected in all Part A and Part B subjects up to and including the Month 12 visits were reported in the 12-Month Clinical Study Report (CSR).

This document is confidential

Statistical Analysis Plan

After the Month 12 DBPCFC, all subjects from Part A and Part B were to continue treatment with active Viaskin Milk 500 μ g, the highest dose determined to be safe, for up to a maximum of 36 months (DBPCFCs at Month 24, 36 and 48). Following results of the 12-month blinded period, all eligible subjects who wish to continue participation in the study switched from Viaskin Milk 500 μ g to Viaskin Milk 300 μ g for 24 additional months of treatment, as per protocol Amendment 5, independently of the duration of previous treatment (Optional DBPCFC at 12 and/or 24 months after switch to Viaskin Milk 300 μ g dose).

A final End-of-Study (EOS) visit will be performed for all subjects when they completed or stopped the study. The EOS visit was to take place 2 weeks after the last DBPCFC at Month 24 for the subjects completing the study at Month 24, or 2 weeks after the last DBPCFC at Month 48, for subjects completing the study extension at Month 48. For subjects switching to Viaskin Milk 300 μ g, the EOS visit will take place 2 weeks after the end of the 24-month treatment period at this dose.

Three-hundred-and-eight children and adolescent subjects have been screened, 198 were randomized in this study, 18 subjects in Part A and 180 subjects in Part B. In Part B, the randomization was stratified by site and by age group (children 2 to 11 years old at the time of Visit 1; adolescents 12 to 17 years old at the time of Visit 1).

The total duration of the study will be approximately 6 years and the total duration of participation in the study will differ for each individual subject and could be up to approximately 6 years.

[Figure 1](#) of the study protocol version 6.0 presents a summary of the enrolment process into Part A and Part B of the study, and [Figures 2](#) and [3](#) present the overview of the study design.

3.2 SUBJECT SELECTION

3.2.1 Inclusion Criteria

Please refer to the respective section of the study protocol version 6.0 for complete information of the inclusion criteria.

3.2.2 Exclusion Criteria

Please refer to the respective section of the study protocol version 6.0 for complete information of the exclusion criteria.

3.2.3 Eligibility Criteria for Study Extension with Viaskin Milk 500 μ g

Please refer to the respective section of the study protocol version 6.0 for complete information of the eligibility criteria for study extension with Viaskin milk 500 μ g. Note: following results of the 12-month blinded period, Month 24 DBPCFC should not be performed anymore.

This document is confidential

[figure not shown]
Statistical Analysis Plan

3.2.4 Eligibility Criteria for the switch to Viaskin Milk 300 µg

Please refer to the respective section of the study protocol version 6.0 for complete information of the eligibility criteria for study extension with Viaskin milk 300µg.

3.3 DETERMINATION OF SAMPLE SIZE

CCI

3.4 TREATMENT ASSIGNMENT & BLINDING

3.4.1 Part A

In Part A, subjects were randomized in 3 successive cohorts of 6 subjects each to receive Viaskin Milk or placebo in a 2:1 ratio. The safety of the 3 doses of Viaskin Milk was assessed over a 3-week treatment period for each dose before proceeding to Part B.

The analysis of the cumulative safety data allowed the selection of the 3 Viaskin Milk doses (150µg, 300µg, and 500µg of cow's milk protein) for randomization into Part B of the study. The screening of subjects in Part B of the study continued when the enrolment

This document is confidential

Statistical Analysis Plan

in Part A was complete, however no subject was randomized into, or treated in, Part B before the review of the safety data from Part A has been completed by both the DSMB and the Food and Drug Administration. A pause in the randomization allowed for this safety review to occur and recommendations to be released.

All subjects in Part A continued their randomized blinded treatment at their assigned initial dose of treatment (150 μ g, 300 μ g or 500 μ g Viaskin Milk or placebo) up to Month 12.

After the Month 12 DBPCFC, all subjects in Part A shall continue treatment in an open-label manner for another 12 months with Viaskin Milk at the highest dose selected (500 μ g of cow's milk protein), based on the safety data of Part A.

3.4.2 Part B

3.4.2.1 Method of Assigning Subjects to Treatment Groups

In Part B, 180 additional subjects were randomized (1:1:1:1 ratio) to receive Viaskin Milk 150 μ g, Viaskin Milk 300 μ g, Viaskin Milk 500 μ g or placebo up to Month 12.

All subjects were assigned an identification number at Visit 1. The IWRS randomized all eligible subjects and assigned the appropriate treatment kit. IWRS managed the inventory and assignment of treatment to subjects at the kit level. The site pharmacists dispensed the drug product according to the IWRS recommendations. Subjects at each dose level were randomly assigned to receive either Viaskin Milk or placebo according to a computer-generated randomization code that was produced by an unblinded study statistician at the Contract Research Organization (CRO) in accordance with the Standard Operating Procedures (SOPs) of the CRO. In addition, the randomization to treatment for subjects randomized in Part B were stratified by site and by age group (children 2 to 11 years old at the time of Visit 1; adolescents 12 to 17 years old at the time of Visit 1).

3.4.2.2 Selection of Doses in the Study

Subjects from Part A and Part B continued treatment with active Viaskin Milk for another 12 months in an open-label manner at the highest dose (500 μ g of cow's milk protein) determined to be safe from Part A. The transition from the blinded to the open-label part of the study was performed keeping the blinding until the results of the first 12-month period were obtained.

The primary analysis that was conducted after the 12-month blinded period showed that the Viaskin Milk 300 μ g was the most effective tested dose. No safety concern was identified at any of the investigated doses. Therefore, all eligible subjects were proposed to switch to Viaskin Milk 300 μ g for a further 24 months, independent of the duration of previous treatment with Viaskin Milk 500 μ g or treatment having received during the blinded initial 12 months of study.

This document is confidential

Statistical Analysis Plan

3.4.2.3 Administration of Study Treatments to Subjects

Double-blind, placebo-controlled treatment period up to Month 12

The subjects were randomized to receive either Viaskin Milk (150µg, 300µg, or 500 µg of cow's milk proteins) or placebo from Day 1 (Visit 4) up to Month 12 (Visit 12) during the double-blind treatment period.

Open-label treatment periods with Viaskin Milk 500µg and Viaskin Milk 300µg after Month 12

After the Month 12 DBPCFC, all subjects were to receive Viaskin Milk 500µg up to Month 24. After the Month 24 DBPCFC, all subjects who entered the study extension were to continue to receive Viaskin Milk 500µg up to Month 48.

Following results of the 12-month double-blind treatment period, all eligible subjects were proposed to switch to Viaskin Milk 300µg for additional 24 months, independently of the previous duration of treatment.

3.4.2.4 Daily duration of patch application at the beginning

To increase the safety of subjects at the beginning of the treatment for both double-blind and open-label Viaskin Milk 500µg periods, the daily duration of patch application was as follows:

- 6 hours of daily application during the first week
- 12 hours of daily application during the second week
- 24 hours of daily application from the third week onwards

The switch to Viaskin Milk 300 µg did not require a progressive increase of application duration, and all subjects were able to start with 24 hours of daily application of Viaskin Milk 300 µg.

3.4.3 DBPCFC

The sequence of food challenge formulas on the first day and the second day of the DBPCFCs will also be randomized. Each site was provided with randomization tables at Screening, Month 12, Month 24, Month 36 and Month 48, as well as at Month 12 and Month 24 after switch to 300µg. The unblinded site personnel in charge of the preparation of the food challenge formula was given a password-protected table. For each subject to be challenged, the unblinded site personnel will enter the subject information and the table will populate automatically to determine which formula (Milk or placebo) is given on the first day of the food challenge and which formula (Milk or placebo) will be given the second day of the challenge.

The subject and the assessors will remain blind to the formulas' order during the conduct of the challenge on both days (see Section [7.3.1.1 of the protocol for emergency unblinding procedures](#)). At the end of the second day of the challenge will the order of

This document is confidential

Statistical Analysis Plan

the formulas be unblinded to the subject and the assessors.

3.5 ADMINISTRATION OF STUDY MEDICATION

In [Section 6](#) of the study protocol version 6.0 the complete information of the study drug administration is available.

3.6 STUDY PROCEDURES AND FLOWCHART

The planned study assessments are summarized in the study protocol version 6.0 in [Section 7.4 "Schedule of assessments"](#):

- [Table 2](#) for the first year of treatment (double-blind period),
- [Table 3, 4](#) and [5](#) for the second, third and fourth year of treatment with Viaskin Milk 500 μ g dose (open-label Viaskin Milk 500 μ g period),
- [Table 6](#) and [7](#) for first and second year after the switch to Viaskin Milk 300 μ g dose (open-label Viaskin Milk 300 μ g period).

4 ENDPOINTS

4.1 PRIMARY EFFICACY ENDPOINT

The primary efficacy endpoint was the percentage (%) of subjects who were treatment responders after the first 12 months of EPIT treatment.

A treatment responder is defined as a subject who meets at least one of the following criteria:

- A \geq 10-fold increase in the Cumulative Reactive Dose (CRD) of cow's milk proteins at the Month 12 DBPCFC as compared to baseline value and reaching at least 144 mg of cow's milk protein (approximately 4.5 mL of milk)
- A CRD of cow's milk proteins \geq 1444 mg (approximately 45 mL of milk) at the Month 12 DBPCFC.

The cumulative reactive dose (CRD) of cow's milk proteins is entered directly in CRF by the sites and is calculated as the sum up of all doses of cow's milk proteins given during the challenge, including repeat doses if applicable, and exact quantity of the last dose given (if not given in totality).

This document is confidential

Statistical Analysis Plan

4.2 SECONDARY EFFICACY ENDPOINTS

4.2.1 Double-blind period

- The mean and median CRD of cow's milk proteins at Month 12 and change from baseline.
- The change from baseline value in levels of cow's milk sIgE and sIgG4 at all time points evaluated up to Month 12.
- The change from baseline value in levels of sIgE and sIgG4 to caseins, α -lactalbumin and β -lactoglobulin at all time points evaluated up to Month 12.
- The change from baseline in SPT wheal at all time points evaluated up to Month 12.
- The change in the severity of symptoms elicited during the milk DBPCFC from baseline to Month 12¹.
- The change from baseline in Quality of Life (QoL) assessments at Month 12.

4.2.2 Open-label periods

- The percentage (%) of subjects who are treatment responders over the course of open-label treatment with Viaskin Milk 500 μ g and 300 μ g
- The CRD of cow's milk proteins over the course of open-label treatment with Viaskin Milk 500 μ g and 300 μ g.
- The levels of sIgE to cow's milk over the course of open-label treatment with Viaskin Milk 500 μ g and 300 μ g.
- The levels of sIgG4 to cow's milk proteins over the course of open-label treatment with Viaskin Milk 500 μ g.
- The levels of sIgE and sIgG4 to caseins, α -lactalbumin, and β -lactoglobulin over the course of open-label treatment with Viaskin Milk 500 μ g and 300 μ g.
- The SPT wheal over the course of open-label treatment with Viaskin Milk 500 μ g and 300 μ g.
- The severity of symptoms elicited during the milk DBPCFC over the course of open-label treatment with Viaskin Milk 500 μ g and 300 μ g
- The QoL assessments over the course of open-label treatment with Viaskin Milk 500 μ g and 300 μ g.

¹ Grading of symptoms will be done using the grading definition in the OFC Symptom Score Sheets.

Statistical Analysis Plan

4.3 SAFETY ENDPOINTS

- Treatment-Emergent Adverse Events (TEAEs) by system organ class, preferred term, maximum severity, and relatedness to the investigational product.
- Serious Adverse Events (SAEs) and Treatment-Emergent Serious Adverse Events (TESAEs) by system organ class, preferred term, severity, and relatedness to the investigational product.
- TEAEs leading to study discontinuation, and relatedness to the investigational product.
- Incidence, duration, and maximum severity of local cutaneous reactions, as assessed by the subject.
- Severity of local cutaneous reactions, as assessed by the Investigator.
- Adverse Events of Special Interest (AESI) including systemic² allergic symptoms and local AESI.
- Frequency and severity of symptoms elicited during the DBPCFC.
- Vital signs, physical examinations, and laboratory data.
- Spirometry and Peak Expiratory Flow (PEF) data.

4.4 EXPLORATORY ENDPOINTS

- The change from baseline in epigenetic modifications at Month 12, if evaluated.
- Epigenetic modifications over the course of open-label treatment with Viaskin Milk 500 µg and 300 µg, if evaluated.
- The relationship between the presence of filaggrin mutations, safety, and response to treatment.
- The change from baseline value in levels of sIgE to peanut, egg, house dust mite, and grass pollen.
- Enumeration and characterization of reactions triggered by accidental consumption of cow's milk (in any form) during the study.
- Analysis of "risk-taking behaviour" of subjects (voluntary milk consumption) during the study.
- Planned management of the subject after termination of the study.

²Events are considered as systemic unless there is evidence in the event term or coding information that the reaction is only extended around the patch area.

Statistical Analysis Plan

5 ANALYSIS SETS

5.1 INTENT-TO-TREAT SET (ITT)

The Intent-to-Treat Set includes all randomized subjects. Subjects will be analyzed according to randomized treatment.

The ITT Set will be used for all analyses of efficacy endpoints during the double-blind period.

5.2 PER PROTOCOL SET (PPS)

The Per Protocol Set includes all subjects from the ITT population who do not have major protocol violations that may affect the primary endpoint. This population will be analyzed according to study treatment that was actually received by the subjects.

Protocol deviations occurring during the randomized blinded treatment period were categorized as either major or minor at the (Blind) Data Review Meetings (BDRM). A corresponding listing was prepared for review in order to determine the subjects to be excluded from the ITT, and hence did not belong in the Per Protocol set. Manual protocol deviations were also collected and considered at the BDRM. BDRM specifications are described in separate specific document. Decisions taken at the BDRM were documented and approved by DBV prior to database lock and unblinding the study.

Protocol deviations may include but are not limited to:

- Informed Consent / Assent
- Inclusion / Exclusion Criteria
- Investigational Product Administration
- Visit Schedule
- Procedures / Tests
- Concomitant Medications
- Adverse Events / Serious Adverse Events
- Food Challenge
- Other

Protocol deviations due to Corona Virus Disease 2019 (COVID-19) are added in 2020:

- Missed or out-of window visits due to COVID-19
- Missed assessments due to COVID-19
- Direct-to-Patient shipment of IMP due to COVID-19

5.3 SAFETY SET (SS)

The Safety Set includes all subjects who applied at least 1 Viaskin patch. Subjects will be analyzed according to treatment received. In case of wrong dispensation, the subject

This document is confidential

Statistical Analysis Plan

will be analyzed according to the treatment received the longest, or as will be determined at the BDRM, on a case-by-case basis.

The safety set will be used for all safety analysis tables and listings, which include the randomized blinded treatment period.

5.4 OPEN-LABEL SET 500 (OLS-500)

The Open-Label Set 500 includes all subjects who entered the open-label treatment period and applied at least one Viaskin Milk 500 μ g patch during the open-label period.

Analyses of the Viaskin Milk 500 μ g open-label treatment period was performed on the OLS-500.

5.5 PER PROTOCOL OPEN-LABEL SET 500 (PPS-500)

The Per Protocol Open-Label Set 500 includes all subjects from the OLS-500 population who do not have major protocol violations that may affect the main efficacy endpoint.

Protocol deviations occurring during the Viaskin Milk 500 μ g open-label treatment period were categorized as either major or minor at the Data Review Meeting (DRM). A corresponding listing was prepared for review in order to determine the subjects to be excluded from the Per Protocol Open-Label Set 500 (PPS-500). DRM specifications were described in separate specific document.

5.6 OPEN-LABEL SET 300 (OLS-300)

The Open-Label Set 300 will include all subjects who entered the open-label treatment period after switch to Viaskin Milk 300 μ g and applied at least one Viaskin Milk 300 μ g patch during this open-label period.

Analyses of the Viaskin Milk 300 μ g open-label treatment period will be run on the OLS-300.

5.7 PER PROTOCOL OPEN-LABEL SET 300 YEAR 1 (PPS-300 YEAR 1)

The Per Protocol Open-Label Set 300 Year 1 will include all subjects from the OLS-300 population who do not have major protocol violations during the first year of Viaskin Milk 300 μ g open-label treatment period that may affect the efficacy evaluation of the open-label 300 μ g dose during the first year.

Respective protocol deviations will be categorized as either major or minor at the Data Review Meeting (DRM).

A corresponding listing will be prepared for review in order to determine the subjects to be excluded from Per Protocol Open-Label Set 300 Year 1. DRM specifications are described in separate specific document.

This document is confidential

Statistical Analysis Plan

5.8 PER PROTOCOL OPEN-LABEL SET 300 YEAR 2 (PPS-300 YEAR 2)

The Per Protocol Open-Label Set 300 Year 2 will include all subjects from the OLS-300 population who do not have major protocol violations during the second year of Viaskin Milk 300µg open-label treatment period that may affect the main efficacy evaluation of the open-label 300µg dose during the second year.

Respective protocol deviations will be categorized as either major or minor at the Data Review Meeting (DRM).

A corresponding listing will be prepared for review in order to determine the subjects to be excluded from the OLS-300 Year 2. DRM specifications are described in separate specific document.

6 GENERAL ASPECTS FOR STATISTICAL ANALYSIS

6.1 GENERAL METHODS

6.1.1 General

All analyses and summaries will be produced using CCI [REDACTED]

Unless otherwise specified, summaries will be presented overall and for each age group, in total and by treatment (placebo/dose level/overall active). "Overall active" is a synonym for "All Doses Viaskin Milk". In the OL-period(s) analyses, it is defined as the subjects who were randomized / treated in one of the 3 Viaskin Milk doses for the double-blind treatment period.

The secondary and explorative efficacy endpoints, referring to "Change to Baseline" are all analyzed with respect to "Month 0". If not specified otherwise, summaries for changes from baseline indicate summaries relative to "Month 0" as well as relative to "Month 12", see [section 6.2.1](#) for definition.

Unscheduled assessments will not be included in summary tables unless specified otherwise, but will be included in the subject listings.

In case of repeated measurements in the scheduled time-windows, the first measurement will be used for analysis, if not specified otherwise.

Early termination assessments will be analyzed as having occurred at the next scheduled assessment.

All tables, listings and figures will include footers that identify the name of the program that created the item, together with the date and time on which it was created. Headers will include the total number of pages that the presentation contains and, for each page, the number of the page within the presentation.

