7.3.2.8 Physical Examination and Skin Reaction Grading

Physical examination will include, but is not limited to, head, eyes, ears, nose, and throat (HEENT), as well as a complete examination of the skin, and will be performed at each visit (see [Table 2 to Table 7](#)), before the DBPCFC, and during the DBPCFC at the Investigator's discretion, when applicable.

Local skin reactions of the area of the skin used for application of the Viaskin patch on the arms (adolescents and former adolescents who become adults) or back (children) will be graded (Table 1) by the same Investigator at each visit if possible, according to the slightly modified recommendations of the EAACI/GA²LEN position paper.²⁵

Table 1: Skin Reaction Grading System

Grade	Skin Reaction
Grade 0	Negative
Grade 1	Only erythema, or erythema + infiltration
Grade 2	Erythema, few papules
Grade 3	Erythema, many or spreading papules
Grade 4	Erythema, vesicles

Viaskin patches are transparent and the degree of local reactions can be easily seen through the patch. Grades of local skin reactions on the arms or the back will be recorded in the eCRF when subjects arrive at the site for a visit.

If Grade 4 local skin reactions are observed, patch application should be transiently interrupted and the subject should visit the site for the next application (see [Section 6.3.2](#)).

Photographic records will be taken of the site(s) of application of the Viaskin patch and filed in the subject's medical records or source documents and provided to the CRO or sponsor as necessary upon request.

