8.1.7 Safety Variables

Safety endpoints will include the following:

- AEs and TEAEs by system organ class, preferred term, maximum severity, and relatedness to the investigational product.
- SAEs and TESAEs by system organ class, preferred term, severity, and relatedness to the investigational product.
- TEAEs leading to study discontinuation, and relatedness to the investigational product.
- Incidence, duration, and maximum severity of local cutaneous reactions, as assessed by the subject.
- Severity of local cutaneous reactions, as assessed by the Investigator.
- AESI including systemic allergic symptoms and local AESI
- Frequency and severity of symptoms elicited during the DBPCFC.
- Vital signs, physical examinations, and laboratory data.
- Spirometry and PEF data.

In all safety presentations, imputation of missing data will take the option of the most conservative outcome, so that, for example, missing relatedness for a TEAE will be assumed to be related and missing severity will be assumed to be severe if the severity is missing for an AE starting on or after the date of initial Viaskin Milk patch application and mild if the severity is missing for an AE starting prior to the date of initial Viaskin Milk patch application.

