8.1.7.3 Physical Examination and Patch Site Examination

Physical examination results, including complete observation of the skin will be listed and summarized overall and by age group, visit, timepoint, and dose level/placebo group on the SS for the randomized blinded treatment period (Months 0 to 12).

Physical examination during the open-label treatment periods after Month 12 will be described. Details will be provided in the SAP.

In addition, examination of the skin at the site of Viaskin patch application will be graded from Grade 0 (negative) up to Grade 4 (erythema, vesicles). These results will be summarized using descriptive statistics and presented overall and by age group, visit, dose level and placebo group in the SS for the randomized blinded treatment period (Months 0 to 12). Worst grade reported by subject for blinded treatment period and open-label treatment period will also be tabulated.

Examination of skin at patch site during the open-label treatment periods after Month 12 will be described. Details will be provided in the SAP.

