9.7.2 Double-blind Month 12 and OL-500 analyses

These results were summarized using descriptive statistics and presented overall and for each age group and visit in total and by treatment group (placebo/dose level/overall active) on the SS for the randomized blinded treatment period.

These analyses were repeated overall and for each age group and visit in total and by initial actual treatment group on the OLS-500, for the Viaskin Milk 500 μ g open-label

This document is confidential

Statistical Analysis Plan

treatment period. Similarly, the last value in Viaskin Milk 500 μ g open-label treatment period were summarized.

Worst grades reported for any treatment period will also be tabulated.

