9.7.3 OL-300 Analyses

The grades will be summarized using descriptive statistics and presented overall and for each age group and visit in total and by initial actual treatment group (placebo/dose level/overall active) on the OLS-300 for the analyzed OL-300 period.

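### Under the SAP's default, the worst patch-site grade table would miss Grade 4 reactions graded only at unscheduled visits, and SAP 9.7.3 names no such table for OL-300

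*SAP*

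**What the plan says.** SAP 6.1.1 gives two defaults that apply to every table unless a section overrides them. The first is "Unscheduled assessments will not be included in summary tables unless specified otherwise, but will be included in the subject listings". The second is "In case of repeated measurements in the scheduled time-windows, the first measurement will be used for analysis, if not specified otherwise".

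SAP 9.7 covers the investigator's grading of the skin under the patch, from 0 to 4. For the double-blind and OL-500 analyses, 9.7.2 describes by-visit summaries and adds "Worst grades reported for any treatment period will also be tabulated". For OL-300, 9.7.3 says only "The grades will be summarized using descriptive statistics and presented overall and for each age group and visit". No part of 9.7 mentions unscheduled gradings.

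In the protocol, section 8.1.7 lists as a safety endpoint "Severity of local cutaneous reactions, as assessed by the Investigator", and section 8.1.7.3 states "Worst grade reported by subject for blinded treatment period and open-label treatment period will also be tabulated". For Grade 4, section 7.3.2.8 says that "patch application should be transiently interrupted and the subject should visit the site for the next application". Sections 6.3.1 and 6.3.2 give the same instruction and add that the affected zone is to be examined at that visit. Section 7.3.2.8 also has the grade entered in the eCRF on arrival at a site visit.

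**The concern.** A visit made because of a Grade 4 reaction is not in the schedules of assessments (protocol Tables 2 to 7), so its grading is unscheduled. Under the 6.1.1 default that grade goes to the listings and not to a summary table. For a by-visit table this is sensible. For a worst-grade table it is not, because the excluded gradings are those obtained because the reaction was severe.

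At stake is the summary of a named safety endpoint at its most informative level. Grade 4 means vesicles, and protocol 7.3.2.5 lists any Grade 4 patch-site reaction as a local AESI. The subject diary does not fill the gap: SAP 9.10.2 summarises it for the first 3 months only, and it grades itching, redness and swelling. The worst-grade table is the planned per-subject summary of the investigator's 0-to-4 scale.

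A second gap stands apart from the question of unscheduled visits: no worst-grade table is named in the OL-300 section.

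**Working it through.** The documents state no figure to reproduce. The check sets the passages side by side.

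**1. Does SAP 9.7 override the default?** No explicit override appears in 9.7.1, 9.7.2 or 9.7.3. Where the SAP wants unscheduled data to count, it says so: SAP 6.2.1 defines both Month 0 and LV-OL-500 as the latest available assessment and names scheduled and unscheduled assessments together.

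**2. Does the plan generate unscheduled gradings?** Yes. Protocol 6.3.1, 6.3.2 and 7.3.2.8 send Grade 4 reactions to a site visit (in the open-label periods, other local AESIs as well), and a grade is entered there.

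**3. Which way would the error run?** A maximum over some of the gradings can only equal or fall below the maximum over all of them. Leaving gradings out can lower a subject's worst grade but never raise it.

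**4. Which reactions would be missed?** Only those that reach Grade 4 and heal between scheduled gradings. A Grade 4 first seen at a scheduled visit is counted. The spacing is:
- Blinded year, target days in SAP Table 3: 91, 182, 274, 365. The gaps are 182 − 91 = 91, 274 − 182 = 92 and 365 − 274 = 91 days.
- OL-300, protocol Tables 6 and 7: after the switch visit, gradings common to all subjects on treatment are at Months 6, 12, 18 and 24, so about 6 months apart.

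**5. The first-measurement rule.** It selects by order and not by severity, so it would not bring in a later, worse grade from the same window.

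**6. Illustration only.** Assume an episode of L days, starting at random in a period of T days with k scheduled gradings. The chance that a scheduled grading falls inside it is roughly kL/T. The documents support neither the length nor the random onset; L = 7 and L = 14 are assumed.

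| Period | k | T | L = 7 | L = 14 |
|---|---|---|---|---|
| OL-300 | 4 | 730 | 28/730 = 3.8% | 56/730 = 7.7% |
| Blinded, V12 and V13 as one occasion | 7 | 365 | 49/365 = 13.4% | 98/365 = 26.8% |
| Blinded, V12 and V13 separate | 8 | 365 | 56/365 = 15.3% | 112/365 = 30.7% |

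Protocol Table 2 has patch-site gradings common to both parts after Day 1 at V6 to V13, which is 8. V12 and V13 are normally within 7 days of each other, with no patch worn between them, so they are close to one occasion. Reactions that cluster early, when visits are frequent, would be caught more often. The table shows how the result moves with the assumption. It does not estimate what was lost.

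**7. Is there an OL-300 worst-grade table?** SAP 9.7.3 presents grades "for each age group and visit in total and by initial actual treatment group" and stops there. The worst-grade sentence sits in 9.7.2, under the heading for the double-blind and OL-500 analyses. Other OL-300 sections (8.2.5.2, 9.3.4.2) say explicitly that earlier summaries are repeated. Protocol 8.1.7.3 asks for the worst grade in the open-label period, and SAP 12.6 records no change from the current protocol.

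**The case against.** The strongest objection is that the worst-grade table is defined by period and not by visit. Worst grades reported for a treatment period can naturally be read as covering every grade reported in it. The same sentence is in the future tense and refers to any treatment period, and OL-300 is a named period in SAP Table 1, so it may be meant to reach OL-300 too. The table mock-ups are separate documents and could settle both questions. This stands as a possible reading. It does not remove the problem, because 6.1.1 sets the opposite default and two programmers following the SAP could produce different tables.

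The second objection is that Grade 4 reactions are captured elsewhere. As local AESIs they enter the overview and incidence tables in SAP 9.3.3, repeated for OL-300 in 9.3.4, and the unscheduled gradings remain in the listings. This stands: the information is displaced, not lost. How complete the AESI retrieval is cannot be checked, because the appendix describing it is blacked out in the public copy.

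Third, the protocol describes Grade 4 as rare, so few subjects may be affected. That is fair, although in a worst-grade table those few subjects are the ones that matter.

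A reader might go further and infer that the existing tables leave out most Grade 4 reactions, or that the reported skin safety of the blinded year is biased. The documents do not support either. They do not show how the table was programmed, they give no incidence, and any percentage rests wholly on an assumed episode length and onset.

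**Conclusion.** The point holds as a gap in specification with a known direction and an unknown size. If the 6.1.1 default is applied as written, a Grade 4 reaction graded only at an unscheduled visit is missing from the investigator-graded worst-grade table, and the error can only make reactions look milder. This rests on two readings: that the reaction-driven visit counts as unscheduled, which follows from its absence from the schedules, and that 9.7.2 does not itself override the default, which is arguable. By-visit tables restricted to scheduled visits are not at fault.

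The missing OL-300 table is a separate and simpler point. Protocol 8.1.7.3 requires a worst grade for the open-label period, and SAP 9.7.3 does not name one.

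The double-blind and OL-500 analyses are described in SAP section 2 as already run, so the practical weight falls on the OL-300 and final analyses.

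**What to change.** - In SAP 9.7, state that the worst grade per subject and period is taken over all investigator gradings in that period, scheduled and unscheduled. This overrides both defaults in 6.1.1 for this table.
- In SAP 9.7.3, add the worst-grade table for OL-300 on the OLS-300.
- Leave the by-visit tables on scheduled visits, and align the table mock-ups.
- Apply this prospectively to the OL-300 and final analyses. For the double-blind and OL-500 periods, check whether unscheduled gradings were left out. If they were, add a supplementary worst-grade table and leave the completed one in place.

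The cost is two sentences and one derivation, using grades already in the eCRF. The worst-grade distribution may look slightly less favourable. The change concerns reporting only and alters no clinical rule.
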